### 7.4 SCREENING AND RECRUITMENT OF SUBJECTS

Patients with prescription of opioids will be identified based upon a register of primary health care indicator: "Lm12alla"(20). The list of possible subjects will be randomized and 10 at a time will be contacted, informed about the study and asked about participation via 1177 and a letter and, if no answer, by phone after a few days. Patients fulfilling the criterions of inclusion will be informed by phone and those who express interest in participating will be invited to a first visit at the health care center (index appointment).

The following information will be recorded in the participant's electronic health record (Cosmic): Trial name, date when signed informed consent was obtained, PI's contact information.

## 8 TREATMENT OF SUBJECTS

### 8.1 PHASE 1 (INVESTIGATION AND ASSESSMENT, WEEK 1-3):

- A medication review focusing on pain, sleep and depression/anxiety disorders according to the Swedish National Board of Social Affairs and Health HSLF-FS 2017:37 will be implemented by a pharmacist (21). This includes patient consultation to reconcile what medications the patient is using and has used before in relation to pain, sleep and depression/anxiety, and to identify potential drug-related problems (non-compliance, side effects, interactions, etc.).
- A thorough pain analysis is conducted by a GP according to existing guidelines including duration of pain, pain localization and pain mechanisms (4).

- A visit to a physiotherapist for evaluation and assessment of possible treatment regarding physical exercise/physical activities and related treatments.
- A visit to a psychologist for diagnostics and treatments regarding psychological and social factors.
- A person-centred approach is adopted in all patient consultations. In person-centred care the patient narrative is essential to invite the patient to a partnership including the person, not only the disease but how the disease affects the individuals' life as a whole. Decision on a rehabilitation plane should rest on a partnership between the person and health care, which includes sharing of information and a shared decision-making about treatment. To ensure a safe partnership, the patient's narrative but also the responsibilities of both parties (patient and health care) as well as the rehabilitation plane is documented and transparent for all parts(22).

#### Phase 2 (treatment plan, vecka 3-4):

- An appointment with all healthcare personnel involved in Phase 1 including the patient where an individualized rehabilitation plan is set up based on the biopsychosocial model of pain and in accordance with treatment recommendations in the national clinical knowledge support, including aims, interventions and a follow-up plan (4,23). The rehabilitation plan will be based on the patient's needs and conditions (e.g., a plan of opioid tapering including follow-up by the pharmacist) and documented in the participant's electronic health record by the care manager. The rehabilitation plan will be available to the participant through the electronic health record or printed out, based on what is suitable for the participant.

#### 8.2 PHASE 3 (TREATMENT AND FOLLOW-UP, WEEK 4-24):

- Implementation of the individualized rehabilitation plan.
- Frequent follow-up contacts (1 per 1-3 weeks) by phone with an established care manager, i.e. contact person (one of the team staff or a rehabilitation coordinator or a nurse) with a person-centred approach. The care manager's responsibility will be to ensure that health services meet their commitments in the care plan and to serve as a main point of contact between participants and health care.
- An appointment with all health care personnel involved in the rehabilitation plan, 3-4 months after the start of phase 2 to update the plan.

#### 8.3 CONTROL: USUAL CARE

Participants in the control healthcare centres will receive usual care. This may include appointments and treatment by a GP, nurse, physiotherapist and/or psychologist. No pharmacist will be working at the healthcare centre. However, NVH does provide centralized medication review services to all primary healthcare centres in Region Uppsala. Any healthcare professional may request a medication review by a pharmacist on a work-from-home basis as part of usual care.

## **9 ENDPOINTS AND OUTCOME MEASURE ASSESSMENT**

### **9.1 PRIMARY ENDPOINT**

Pain interference as measured with the Brief Pain Inventory – Short Form (BPI-SF)(24), question number 9 a-g. The primary outcome measure will be the difference in pain interference after 3, 6 and 12 months. A text message will be sent one week in advance to the digital link, and in case of missing data, a telephone call will be made as a reminder

### **9.2 SECONDARY ENDPOINTS**

Secondary endpoints will be pain intensity (as measured with BPI-SF, question number 3-8), symptoms of depression (Patient Health Questionnaire-9; PHQ-9), symptoms of anxiety (General Anxiety disorder-7; GAD-7), patient satisfaction (Patients' Global impression of Change; PGIC), quality of life (EQ-5D-5L), opioid use (morphine equivalents) and symptoms of withdrawal (Short Opioid Withdrawal Scale; SOWS). All outcomes in the intervention study are based on internationally recognized IMMPACT-guidelines(25). Secondary endpoints will be measured after 3, 6 and 12 months, including pain interference at these time points.

## **10 PROCESS EVALUATION**

### **10.1 FEASIBILITY STUDY**

The aim with the process evaluation unlike the feasibility is to explore the process and not only the feasibility. If the process is performed as planned, why the process works or not and in which context. What can improve to get a more optimized intervention. Factors related to the implementation of the intervention will be investigated. This will include individual interviews with all patients and one semi-structured follow-up focus groups with health care staff. Questions about the participants' experience, success factors, barriers and suggestions for improvement are made by the researchers, which are then reported in text and tabular form. To examine the process during the intervention, semi-structured observations will be carried out for all care visits. Person-centred and team-based care are two factors to observe during the study. The result will be presented in text and tabular form. Patient recruitment data, completed intervention components data in term of fidelity, adaption, dose, reach and strength will be presented with descriptive statistics. The number and reasons for drop outs will be reported and analyzed descriptively. An expected duration of patient recruitment for the intervention

study will be calculated based on the feasibility. Based on the above results, the study protocol for the planned intervention study will be updated.

## 10.2 PROCESS EVALUATION DURING TRIAL

Similar to the feasibility study data collection and analysis above, a process evaluation according to the British Medical Research Council framework will be conducted to analyse implementation, protocol adherence and participants' experience and opinions(26,27) . The process evaluation includes evaluation of the training from the perspective of the healthcare staff in questionnaire and interview form.

Furthermore, a continuous follow-up of the three phases of the intervention will be done, above all if and when they are carried out (protocol adherence) and how they work by performing observations. In addition, questionnaires' and focus groups, or semi-structured interviews, will be held with the healthcare staff who carried out the intervention, as well as the operations manager at the participating healthcare centres. This is to identify success factors and areas for development. A heterogeneous sample of patients will be interviewed within one month of undergoing the intervention. These interviews deal with the patients' experiences of the intervention, as well as their suggestions for further development and implementation of the intervention. The process evaluation will be analysed descriptively and through qualitative content analysis as above. The process evaluation for the trial may come and change after the feasibility study.

## 11 TRIAL ASSESSMENTS AND PROCEDURES OVERVIEW

All trial assessments and procedures are viewed in Figure 1.

Time (months)	Index (0)	1,5	3	6	12
Inclusion:					
Screening in- and exclusion criteria	X				
Informed consent	X				
Interventions:					
Intervention: phase 1-3	↔	↔			
Control: usual care	↔	↔			
Data collection (intervention study):					
Baseline characteristics	X				
Pain interference (BPI-SF)	X	X	(X)*	(X)*	
Pain intensity (BPI-SF)	X	X	(X)*	(X)*	
Symptoms of depression (PHQ-9)	X	X	(X)*	(X)*	
Symptoms of anxiety (GAD-7)	X	X	(X)*	(X)*	
Patient satisfaction (PGIC)		X	(X)*	(X)*	
Quality of life (EQ-5D-5L)	X	X	(X)*	(X)*	

Self Efficacy(PSEQ-2)	X		X	(X)*	(X)*
Data collection (process evaluation):					
Process outcomes (intervention fidelity)		X	X	(X)*	(X)*
Interviews (patients)				X	
Focus group discussion (not all participants)				X	
Observation	←	→			

**Figure 1.** Schedule for inclusion, interventions and data collection according to the SPIRIT statement.

\* Study participants in the feasibility study will possibly be asked to be part of the later intervention study where follow-up also takes place after 6, 9 and 12 months. This requires new informed consent from the study participant. BPI-SF = Brief Pain Inventory - Short form; EQ-5D-5L = EuroQol 5-dimension 5-level version; GAD-7 = General Anxiety Disorder-7; PGIC = Patients' Global Impression of Change; PHQ-9 = Patient Health Questionnaire-9; SOWS = Short Opiate Withdrawal Scale.

## 12 STATISTICS AND DATA MANAGEMENT

### 12.1 DATA MANAGEMENT

Data management will be handled as described in separate Data Management Plan

### 12.2 STATISTICAL ANALYSIS

Primarily, statistical analyses will be conducted based on intention-to-treat (ITT) principle. Patient characteristics will be presented descriptively per treatment group. The average value of pain interference and quality of life in accordance with BPI-SF will be calculated and analyzed separately per treatment group. The difference between the intervention group and the control group will be analysed through regression analysis including the ability to adjust for base line data and other covariates. ANOVA for repeated measurements will be used to analyse the average differences between the two groups until 12 months. The number of dropouts will be reported and analysed descriptively. All randomized study subjects completing the whole study period (complete cases) will be analyzed Per Protocol. For a specific analysis, study subjects with missing data on any of the variables in the model will be excluded from the analysis. Analyses of this population is seen as sensitivity analysis to investigate whether conclusions are sensitive to assumptions regarding the pattern of missing data. All analyses will be described in a prespecified statistical analysis plan (SAP). Significance tests will be two-tailed and a p-value less than 0.5 will be interpreted as significant. All statistical analyses are carried out in an SPSS, SAS or R. The process evaluation is analysed descriptively as well as through a qualitative thematic analysis.

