## **6 TRIAL DESIGN AND SETTING**

### **6.1 TRIAL OUTLINE**

The trial is a controlled before-and-after study that has been designed, and will be reported, according to the applicable CONSORT guidelines (19). No randomization or blinding will be involved. A feasibility study will be conducted prior to the full trial.

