### **6.2 SETTING AND SITE SELECTION**

This study will be conducted at eight healthcare centres in Region Uppsala, NVH. At four of the healthcare centres a new person-centred team-based treatment model including pharmacists (intervention) will be implemented. Basic conditions for these healthcare centres are the accessibility of at least one person of each healthcare profession: pharmacist, GP, psychologist and physiotherapist, where one of these (or a rehabilitation coordinator or a nurse) takes the role of care manager. Healthcare personnel will receive special training in person-centered care and managing patients diagnosed with chronic pain before the study. In addition, four control healthcare centres without a pharmacist will be matched with the intervention healthcare centres

according to according to geographic area (urban, suburban, or rural) and the size of the centres (number of listed patients). No specific efforts for implementation will be made in these control centres.

Patients being participants at the intervention health care centres will start their inclusion in the new person-centred team-based treatment immediately at the index appointment and up to 24 weeks. Participants at the control centres will receive usual care.

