### 12.3 DETERMINATION OF SAMPLE SIZE

The power calculation (and thus the sample size) is based on the assumption that the data are approximately normally distributed. We assume that the patient size in both treatment groups will be the same, 1:1. Based on previous studies and unpublished data from the U-PAIN cohort we assume that the baseline value (index visit) for the primary outcome is 6,0 in both treatment groups. We consider a difference in change of 1,0 between the groups at 12 months to be clinically relevant and assume that the standard deviation of the change is 1,43. To detect a difference of 1.0 in pain interference between the two groups with a power of 90% and a type-1 error of 5%, 46 participants in each treatment group is required. With regard to dropouts (20%) we aim for at least 55 participants per treatment group (110 in total). Based on the current patient count calculation (90% power and  $\alpha = 0.05$  to detect a 1.0 difference in the primary outcome measure) based on previous studies (16) and data from the U-PAIN cohort (28), we aim in the intervention study for at least 55 study participants per treatment group (110 in total).

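### Baseline adjustment is optional in a non-randomised comparison powered on change, and the repeated-measures ANOVA names neither a baseline term nor a group-by-time contrast

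*Protocol*

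**What the plan says.** Protocol section 12.2 names two methods for comparing the groups and does not say which is primary. The first is "regression analysis including the ability to adjust for base line data and other covariates". The second reads "ANOVA for repeated measurements will be used to analyse the average differences between the two groups until 12 months". The section does not say whether the index visit enters the ANOVA as a time level or a covariate, or which term is tested. It sends the detail of all analyses to a prespecified SAP, which is not shown.

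Other sections bear on this:
- Section 6.1: "No randomization or blinding will be involved".
- Section 6.2: "four control healthcare centres without a pharmacist will be matched with the intervention healthcare centres". The matching uses area type and centre size; the synopsis adds socioeconomic setting. All are centre-level features.
- Section 9.1: "The primary outcome measure will be the difference in pain interference after 3, 6 and 12 months".
- Section 12.3: "We consider a difference in change of 1,0 between the groups at 12 months to be clinically relevant", with an SD of change of 1.43. Also, "we assume that the baseline value (index visit) for the primary outcome is 6,0 in both treatment groups".
- Section 11: the schedule shows BPI-SF pain interference collected at the index visit.

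**The concern.** In a randomised trial, optional baseline adjustment is mainly a matter of precision. Here it also affects validity. Nothing in the design balances patients' pain interference at entry between intervention and control centres. Section 12.3 assumes equal baselines, and section 12.2 contains no rule that protects the estimate if they turn out unequal.

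The sample size rests on change from baseline, but neither analysis method is tied to change. An analyst could follow section 12.2 to the letter, leave baseline out, and report a difference between centres at entry as an intervention effect, or let one hide a real effect. Because the study is unblinded, leaving that choice open also invites the suspicion that it was made after seeing the data.

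**Working it through.** **Inputs from the Protocol (section 12.3 unless noted).** Target difference in change 1.0; SD of change 1.43; 90% power; type-1 error 5%, two-sided (section 12.2); 46 evaluable and 55 enrolled per group; 20% dropout. Evaluable number used below: 55 × 0.8 = 44 per group.

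**Assumptions.** The baseline to 12-month correlation r is not given; 0.4 to 0.7 is used. SDs are equal at both times. Clustering by centre is ignored.

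**The plan's own figure.** A two-sample t-test on change with effect size 1/1.43 needs 43.96, so 44 per group; power at 44 is 90.0%. The stated 46 is slightly more cautious (power 91.3%). The calculation is therefore one for change from baseline.

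**Entry difference and an unadjusted 12-month comparison.** Suppose there is no true effect and a 0.5-point entry difference persists.
- SD of the score: s = 1.43 / √(2(1 − r)).
- Standard error: SE = s × √(2/44).
- False-positive rate (normal approximation): P(Z > 1.96 − 0.5/SE) + P(Z < −1.96 − 0.5/SE).

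With baseline as covariate, the residual SD is s√(1 − r²), the bias left is 0.5(1 − r), and the same formula applies.

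| r | s | SE | False positives, unadjusted | Bias left with covariate | False positives with covariate |
|---|---|---|---|---|---|
| 0.4 | 1.31 | 0.278 | 43.5% | 0.30 | 21.7% |
| 0.5 | 1.43 | 0.305 | 37.5% | 0.25 | 15.7% |
| 0.6 | 1.60 | 0.341 | 31.1% | 0.20 | 11.4% |
| 0.7 | 1.85 | 0.394 | 24.6% | 0.15 | 8.3% |

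In this scenario the change contrast has no bias, because the entry difference cancels.

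**What each contrast estimates.** Let the true effect be −1.0 at each follow-up and d the entry difference (intervention minus control).
- ANOVA group main effect, follow-ups only, d persisting: −1 + d, which is −0.50 at d = 0.5.
- ANOVA group main effect with index as one of four time points: (d + 3(−1 + d))/4, which is −0.75 at d = 0 and −0.25 at d = 0.5. The dilution occurs even with no imbalance.
- Group-by-time (change) contrast, d persisting: −1.0.

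**Neither remedy is right in every case (d = 0.5, r = 0.5).**

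| Behaviour of the entry difference | Unadjusted 12-month score | Change | Baseline as covariate |
|---|---|---|---|
| Persists | −0.50 | −1.00 | −0.75 |
| Regresses to a common mean | −0.75 | −1.25 | −1.00 |

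**Power for a difference of 1.0 at 44 per group (t-test), r = 0.4, 0.5, 0.6, 0.7.** Unadjusted 12-month scores: 94%, 90%, 83%, 71%. A shortfall against 90% appears only when r exceeds about 0.5.

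**The case against.** The strongest reply is that section 12.2 hands the details to a SAP, and that a covariate list or model contrast missing from a protocol is no fault. The wording on adjustment may only describe what regression can do. The design name and section 12.3 both point to change from baseline. A repeated-measures ANOVA with index as a time level and a test of group-by-time would deal with a persisting entry difference.

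Much of this stands. A reader might infer that the protocol prescribes an unadjusted comparison of 12-month scores. It does not: no such analysis is stated, and the harm arises only if the option is left unused or the group main effect is reported. A reader might also infer that the planned power is lost. The documents do not support that as a general claim, because r is not given and unadjusted power is 90% at r = 0.5 and higher at r = 0.4.

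The reply does not remove the point. The issue is what the protocol itself says: adjustment is optional, and the ANOVA targets an average difference, not an interaction. A SAP could comply with both statements and still leave the entry difference in the main result.

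**Conclusion.** The point holds as a fault in how section 12.2 states the main comparison: it does not require the baseline score to be used, in a non-randomised study powered on change. A persisting 0.5-point entry difference would move an unadjusted 12-month estimate by half the target effect, with the false-positive rates tabulated above. Counting the index visit in the ANOVA main effect would remove a quarter of a true effect of -1.0. The size depends on the assumed r, on 44 per arm, on ignoring clustering, and on an entry difference existing; the documents give no evidence that one does.

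It would go too far to say that covariate adjustment must be the primary model. Under a persisting difference it still leaves bias, while the change contrast is off if the difference regresses to a common mean. Neither removes all confounding. Nor does the point support making the centre matching factors mandatory: with only eight centres, those terms would use up much of the information at centre level.

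**What to change.** In section 12.2, replace the optional wording with a firm rule, for example: *The primary comparison at 12 months will account for baseline BPI-SF pain interference*. Then name one of two forms: baseline as a mandatory covariate, or the group-by-time (change from baseline) contrast, which matches section 12.3. For the repeated-measures model, state how the index visit enters and which contrast is reported, so that a main effect averaging over the index visit cannot be taken as the result. Report the form not chosen as a sensitivity analysis, and say that the two can differ in non-randomised groups and that neither removes all confounding.

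The cost is wording and one extra sensitivity analysis. The baseline score is already collected, and the sample size need not change on this account.

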### 12.2.1 ANALYSIS POPULATION

All eligible subjects will be included in the statistical analyses. Statistical analyses will be conducted based on intention-to-treat (ITT) principle.

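### Section 12.2 promises ITT but names repeated-measures ANOVA and a listwise-exclusion rule of unstated scope; if the main analysis is also listwise, the complete-case check on missing data adds nothing

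*Protocol*

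**What the plan says.** Section 12.2 puts intention to treat first, and section 12.2.1 adds: "All eligible subjects will be included in the statistical analyses". For the group comparison, 12.2 names regression with adjustment for baseline and other covariates, and then: "ANOVA for repeated measurements will be used to analyse the average differences between the two groups until 12 months".

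Three consecutive sentences in 12.2 deal with incomplete data:

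- The first defines a completer set: "All randomized study subjects completing the whole study period (complete cases) will be analyzed Per Protocol".
- The second is the exclusion rule. It opens "For a specific analysis, study subjects with missing data" and continues to the effect that "study subjects with missing data on any of the variables in the model will be excluded from the analysis".
- The third gives the purpose: "Analyses of this population is seen as sensitivity analysis to investigate whether conclusions are sensitive to assumptions regarding the pattern of missing data".

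The protocol names no other analysis for missing data. Dropouts are to be counted and described. Details are deferred: "All analyses will be described in a prespecified statistical analysis plan (SAP").

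Section 12.3 expects 20% dropout and bases the sample size on the 12-month difference in change. Section 9.1 sets the primary outcome at 3, 6 and 12 months. Section 6.1 states: "No randomization or blinding will be involved".

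**The concern.** Two things do not fit together.

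First, the promise to analyse everyone sits beside a method that in its textbook form cannot do so. Standard repeated-measures ANOVA needs every visit from every subject. A person seen at months 3 and 6 but not at month 12 is discarded, although two of the three post-baseline values are in hand. The exclusion sentence does not settle the matter, because its scope is not given.

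Second, the complete-case analysis is meant to show whether conclusions depend on the missing-data pattern. It can do this only if the main analysis uses subjects whom the complete-case set leaves out. If both are listwise, agreement between them is guaranteed or nearly so.

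This matters because the comparison is open and non-randomised, between an intensive programme and usual care. Dropout could plausibly differ between arms and be related to response.

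**Working it through.** **Inputs from section 12.3.** Difference in change 1.0 at 12 months, SD of change 1.43, 90% power, 5% type-1 error, 1:1 groups, 20% dropout, 55 per group.

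**The plan's own figure.** A two-sample t-test needs 44 per group (power 90.0%), and the normal approximation gives 43. The protocol states 46, which has 91.3% power, so its figure is reproduced to within two subjects. Dropout at 20% leaves 55 × 0.80 = 44 per group with a 12-month value, and 55 × 0.20 = 11 without.

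**Who is in each analysis, per arm, with monotone dropout and listwise methods.**

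| Analysis | Subjects |
|---|---|
| 12-month regression | 44 |
| Repeated-measures ANOVA to 12 months | 44 |
| Complete-case set | 44 |

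The three sets are identical, so on the same 12-month comparison the check shows a shift of 0.00 whatever the bias. If those who remain also skip months 3 and 6 independently (assumed 5% or 10% each), the complete-case set is 44 × 0.95² = 39.7 or 44 × 0.90² = 35.6. That is 90% or 81% of the 12-month regression set, so the overlap is still large.

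This does not apply to the earlier time points. If all dropout follows month 3, a 3-month regression keeps 55 per arm; if dropout is spread evenly, it keeps about 51, and a 6-month regression about 48.

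**What an analysis of all available values could recover.** The documents give no visit correlation, dropout by arm or dropout mechanism, so everything in this step is assumed. Large-sample simulation: SD 1.43, visit correlation 0.4 or 0.6, true difference 1.00 at every visit, logistic dropout after month 3 with poorer responders more likely to leave (slope 0.5 or 1.0 per SD, same in both arms). Ranges are over these four settings.

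| Dropout depends on | Dropout, intervention/control | Complete cases | Likelihood |
|---|---|---|---|
| either value | 20%/20% | about 1.00 | about 1.00 |
| 3-month value (observed) | 25%/15% | 1.03 to 1.07 | about 1.00 |
| 3-month value (observed) | 30%/10% | 1.05 to 1.14 | about 1.00 |
| 3-month value (observed) | 10%/30% | 0.86 to 0.95 | about 1.00 |
| 12-month value (unseen) | 30%/10% | 1.13 to 1.23 | 1.09 to 1.20 |
| 12-month value (unseen) | 10%/30% | 0.77 to 0.87 | 0.80 to 0.91 |

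The standard error with 44 per arm is 1.43 × √(2/44) = 0.305. The largest bias under observed-value dropout, about 0.14, is 0.14/0.305 = 0.46 of a standard error. Under unseen-value dropout, the likelihood analysis removes only 13% to 36% of the complete-case bias.

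**Equal dropout rates do not guarantee absence of bias.** A second simulation used 20% in each arm but made dropout outcome-related in the intervention arm only (assumed: correlation 0.6, slope 1.5 per SD, true 12-month difference 1.0). With dropout driven by the observed 6-month value, complete cases gave 1.21, and an estimate using the 3- and 6-month data gave 0.99. With dropout driven by the unseen 12-month value, they gave 1.35 and 1.21.

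**The case against.** The strongest reply is that a natural reading removes most of the problem. The exclusion sentence stands between the one that defines the completers and the one that calls analysis of that population a sensitivity analysis. Read together, the three describe one secondary analysis, and the main analysis remains ITT. That reading also agrees with section 12.2.1. This stands: it is the more natural reading. A reader might go further and infer that the protocol applies listwise deletion to its main analysis and so contradicts its own ITT promise. The text does not support that; it leaves the scope open.

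Second, the SAP, which is not at hand, may specify likelihood estimation or imputation, and the software named can fit such models. This also stands, so the absence of those methods from the protocol is not the point. What remains is that the protocol does name a method, and in its standard form that method discards partly observed subjects.

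Third, if the main analysis uses all available values, comparing it with complete cases contrasts two assumptions and is a common check. Agreed. It is limited, because it does not probe dropout that depends on unseen values, but section 12.2 does not claim that it does.

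Fourth, reminders (section 9.1) and contact with subjects lost to follow-up (section 7.3) should reduce missing data. They should, but section 12.3 still allows for 20%.

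**Conclusion.** The point holds in a conditional form. As named, the methods can drop partly observed subjects against the ITT promise, and the scope of the exclusion rule is unstated. If the main 12-month analysis is listwise and loss is monotone, it and its check rest on the same 44 of 55 per arm, and the check cannot do the task given to it. If the main analysis uses all available data, the check is limited but legitimate.

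A reader might infer from the simulations that the trial's result will be biased. The documents do not support that: they give no dropout by arm and no mechanism. The bias is nil at equal 20% dropout when both arms share one mechanism, and under half a standard error with arm imbalance driven by the observed 3-month value. The larger figures need dropout that depends on unseen values, or a mechanism that differs between arms. The case for change is that the better method is cheap and fits the stated principle. Calling completers per protocol, and calling subjects randomized in a trial that section 6.1 says has no randomisation, are wording faults only.

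**What to change.** In section 12.2:

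1. Replace repeated-measures ANOVA with a baseline-adjusted, likelihood-based linear mixed model using all available 3-, 6- and 12-month values of every enrolled subject, with the 12-month group difference as a contrast. This removes bias from dropout that depends on observed values, but only a minority of it when dropout depends on unseen values.
2. State that listwise exclusion applies only to the complete-case sensitivity analysis. Label that set complete cases instead of per protocol, and replace randomized with enrolled.

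A delta-adjusted analysis, which varies the assumption about the unseen values by arm, is an optional addition for the SAP and not a required correction.

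The cost is a few sentences of protocol text and slightly more programming in the software already named. No new data are needed.
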